7.2 Corticosteroids

Patients will join this study after receiving immunosuppressive regimens of corticosteroids for SR-cGVHD for at least 6 months and will remain on the dose at which they started if considered clinically appropriate by the Investigator.

Corticosteroids should be tapered per institutional guidelines at a rate that is commensurate with resolution of GVHD manifestations. If GVHD flares during the taper of prednisone or methylprednisolone, the dose may be re-escalated at the Investigator's discretion and will not be considered treatment failure, as long as the dose does not exceed the initial starting dose. If the dose required exceeds this threshold, or if the flare is not responsive to increased corticosteroids or multiple flares are observed, then the patient will be considered to have experienced treatment failure and will be withdrawn from study treatment.

Corticosteroids may be taken or administered without food.

7.2.1 Prednisone

Prednisone is a white to off-white, odorless, crystalline powder. Tablets are typically white in color and contain lactose monohydrate, magnesium stearate, microcrystalline cellulose, pregelatinized starch, and sodium starch glycolate. Commonly available dose strengths include 1, 2.5, 5, 10, 20, and 50 mg tablets. Prednisone tablets should be stored in accordance with local prescribing information requirements.

Investigators are responsible for ensuring that patients receive commercially available supplies of prednisone for the duration of the study treatment period, if applicable.

7.2.2 Methylprednisolone

Methylprednisolone sterile powder is an anti-inflammatory glucocorticoid, which contains methylprednisolone sodium succinate as the active ingredient. Methylprednisolone sodium succinate (USP) is the sodium succinate ester of methylprednisolone, and it occurs as a white, or nearly white, odorless hygroscopic, amorphous solid. It is very soluble in water and in alcohol. Methylprednisolone (unreconstituted product or solution) should be stored in accordance with local prescribing information.

Investigators are responsible for ensuring that patients receive commercially available supplies of methylprednisolone for the duration of the study treatment period, if applicable.

CONFIDENTIAL

STUDY DRUG: INCB039110 (ITACITINIB)
FINAL PROTOCOL DATE: 26 OCTOBER 2021

INNOVATIONS STUDY NUMBER: BMT 29
VERSION 4

7.3 Accountability for All Study Drugs

The Principal Investigator (or designee) is responsible for accountability of all used and unused study drug supplies at the site.

All study drug inventories must be made available for inspection by the Sponsor (Innovations) or its representatives and regulatory agency inspectors upon request.

At the end of the study, all Innovations Drug Accountability Record Form(s) will be completed by the site and sent to the Innovations Regulatory Department. Study drug supplies must not be destroyed unless prior approval has been granted by Innovations or its representative. Please contact Innovations regarding disposal of any study drug reserves.

8. DOSE MODIFICATIONS

Patients receiving itacitinib at a dose of 200 mg QD may have their dose reduced to 100 mg QD. Patients who are unable to tolerate itacitinib at a dose of 100 mg QD should be withdrawn from study treatment (see Table 1).

8.1 Criteria and Procedures for Dose Interruptions and Adjustments of Itacitinib

If toxicity occurs, the toxicity will be graded utilizing the NCI CTCAE Version 5 (<http://evs.nci.nih.gov/ftp1/CTCAE/CTCAE>), and appropriate supportive care treatment will be administered to decrease the signs and symptoms thereof. Dose interruptions and modifications may occur for individual study patients based on the emergence or resolution of toxicity.

Treatment with itacitinib may be delayed up to 14 days to allow for resolution of toxicity. Subjects may resume treatment if no medical condition or other circumstance exists that, in the opinion of the Investigator, would make the patient unsuitable for further participation in the study. The Investigator should contact the Study Chair to discuss cases where treatment has been delayed for more than 14 days before restarting treatment.

Because patients may enter the study with compromised bone marrow function, these dose reductions are provided as guidelines (see Table 2). Individual decisions regarding dose reduction should be made using clinical judgment and in consultation with the Study Chair, taking into account relatedness of the AE to the study drug and the patient's underlying condition. Adverse events that have a clear alternative explanation or transient (≤ 72 hours) abnormal laboratory values without associated clinically significant signs or symptoms may be exempt from dose-reduction rules.

CONFIDENTIAL

STUDY DRUG: INCB039110 (ITACITINIB)
FINAL PROTOCOL DATE: 26 OCTOBER 2021

INNOVATIONS STUDY NUMBER: BMT 29
VERSION 4

Table 1 Dose Levels of Itacitinib

Dose Level	Itacitinib
Dose Level +1 ^a	300 mg QD
Starting Dose	200 mg QD
Dose Level -1	100 mg QD
Dose Level -2	Discontinue

a Itacitinib dose will be increased to 300 mg QD (3 x 100 mg tablets) for patients with NR/SD after 2 months of therapy at 200 mg QD

NR = no response; QD = once daily; SD = stable disease

Table 2 Guidelines for Interrupting and Restarting of Itacitinib

Adverse Event	Action Taken
Chemistry	
AST and/or ALT >3.0 × ULN in patients with normal ALT/AST at baseline	
 Interrupt for up to 14 days until the toxicity has resolved to ≤ Grade 1. Exceptions require Sponsor approval. Restart at previous dose. If assessed as related to itacitinib, restart at next lower dose and monitor as clinically indicated. 
NOTE: In patients with GVHD-related chemistry elevations at baseline, contact the Study Chair to discuss clinical management and possible dose reductions.

Total bilirubin elevations that occur in the presence of GVHD response that cannot be attributed to new liver GVHD or concomitant therapy	
Total bilirubin is 3.0 to 5.0 x ULN:
 
 Repeat assessment within 7 days. If elevation persists: 
 Immediately hold or reduce dose by 1 level until bilirubin ≤1.5 x ULN Re-escalate or resume previous dose if the repeat value obtained 7 days later shows no persistent elevation. 
Total bilirubin is >5.0 to 10.0 x ULN:
 
 Repeat assessment within 7 days. If elevation persists: 
 Immediately interrupt until bilirubin is ≤1.5 x ULN. Monitor liver function tests weekly or more frequently as appropriate. Re-escalate or resume previous dose if the repeat value obtained 7 days later shows no persistent elevation. 
Total bilirubin is >10.0 x ULN:
 
 Repeat assessment within 7 days. If elevation persists:

CONFIDENTIAL

STUDY DRUG: INCB039110 (ITACITINIB)
FINAL PROTOCOL DATE: 26 OCTOBER 2021

INNOVATIONS STUDY NUMBER: BMT 29
VERSION 4

Table 2**Guidelines for Interrupting and Restarting of Itacitinib**

Adverse Event	Action Taken
	
 - Interrupt until bilirubin is $\leq 1.5 \times$ ULN. - Re-escalate or resume at reduced dose if the repeat value obtained 7 days later shows no persistent elevation; if >7 days, discontinue treatment and monitor as appropriate.
Total bilirubin elevations that occur in patients with Stage 1/2 liver GVHD that cannot be attributed to worsening liver GVHD or concomitant therapy	
Total bilirubin is $>3.0 \times$ ULN:
 
 • Repeat assessment within 7 days. If elevation persists: 
 - Reduce dose by 1 dose level. - Resume previous dose if bilirubin is $\leq 3.0 \times$ ULN.
Hematology	
ANC is $<0.5 \times 10^9/L$, suspected as unrelated to study treatment (e.g., GVHD, active cytomegalovirus viremia)	
 • Reduce dose by 1 dose level. • Monitor ANC count as clinically indicated. • Resume previous dose if ANC count is $\geq 0.5 \times 10^9/L$ for more than 7 days.
ANC is $<0.5 \times 10^9/L$, suspected as related to study treatment	
 • Interrupt for up to 14 days. • Monitor ANC count as clinically indicated. • Resume at a reduced dose if ANC count is $\geq 0.5 \times 10^9/L$ for more than 7 days. If the patient's ANC count remains at $\geq 0.5 \times 10^9/L$ for more than 7 days after resuming treatment at a lower dose, the previous dose may be resumed.
Platelet count is $<10 \times 10^9/L$, or platelet count has decreased by $\geq 50\%$ from baseline, suspected as unrelated to study treatment	
 • Reduce dose by 1 dose level. • Monitor platelet count as clinically indicated. • Resume at previous dose if platelet count returns to $\geq 20 \times 10^9/L$ for more than 7 days.
Platelet count is $<10 \times 10^9/L$, or platelet count has decreased by $\geq 50\%$ from baseline, suspected as related to study treatment	
 • Interrupt for up to 14 days. • Monitor platelet count as clinically indicated. • Resume at a reduced dose if platelet count returns to $\geq 20 \times 10^9/L$ for more than 7 days. If the patient's platelet count remains at $\geq 20 \times 10^9/L$ for an additional 7 days, the previous dose of may be resumed.
Other Toxicities	
Any Grade 1 or Grade 2 toxicity	
 • Continue treatment and manage the toxicity. • Monitor as clinically indicated.
Any Grade 3 toxicity, if clinically significant and not manageable by supportive care	
 • Interrupt up to 14 days until toxicity resolves to \leq Grade 1. • Restart at same dose; if assessed as related to itacitinib, restart at next lower dose and monitor as clinically indicated.
Any recurrent Grade 3 toxicity at 100 mg	
 • Discontinue study treatment; follow-up per protocol.

CONFIDENTIAL

STUDY DRUG: INCB039110 (ITACITINIB)
FINAL PROTOCOL DATE: 26 OCTOBER 2021INNOVATIONS STUDY NUMBER: BMT 29
VERSION 4

Table 2 Guidelines for Interrupting and Restarting of Itacitinib

Adverse Event	Action Taken
QD dose	Exceptions require Study Chair approval.
Any other Grade 4 toxicity	
 • Discontinue study treatment; follow-up per protocol.

ALT = alanine aminotransferase; Absolute neutrophil count = ANC; AST = aspartate aminotransferase; GVHD = graft versus host disease; LFT = liver function test; ULN = upper limit of normal.

8.2 Adjustments of Corticosteroids

Adjustments or tapering of the dose of corticosteroids should be made at the treating Investigator's discretion.

8.3 Tapering of Itacitinib

If a patient has achieved CR or PR after 6 months of treatment, Investigators may begin to taper the dose of itacitinib by 1 dose level provided corticosteroids have been discontinued for at least 8 weeks following institutional guidelines. Subjects must not be experiencing any Grade 2 or higher hematologic toxicity related to study treatment or symptoms of an active infection.

Investigators wishing to initiate a taper of itacitinib at an earlier time point may do so upon consultation with and approval from the Study Chair.

If GVHD signs/symptoms worsen during the taper of itacitinib, the dose may be escalated by 1 dose level. If the patient requires additional systemic therapy (includes restarting of corticosteroids), then the patient would be considered as having disease progression (PD) and would be withdrawn from study treatment.

8.4 Criteria for Permanent Discontinuation of Itacitinib

A full list of criteria for permanent discontinuation of itacitinib are presented in Section 3.3.

9. RESPONSE EVALUATIONS AND MEASUREMENTS

Response will be evaluated by determining the ORR after 6 months of treatment with itacitinib as defined by NIH Consensus Criteria. In addition, patients' ability to either withdraw or decrease steroids while receiving itacitinib will be evaluated, as will patients' personal assessment of their quality of life.

9.1 2014 NIH Consensus Development Project on Clinical Trials in cGVHD

Patient response (CR, PR, or other [unchanged, mixed response, progression]) based on the 2014 NIH Consensus Development Project on Clinical Trials in cGVHD is the primary activity endpoint for this study (see Appendix H for criteria). Response criteria will be assessed on Day 1 of Cycles 2 through 6, between the end of Cycle 6 and the start of Cycle 7, every odd-numbered cycle thereafter starting with Cycle 9, and at the EOT visit.

CONFIDENTIAL

STUDY DRUG: INCB039110 (ITACITINIB)
FINAL PROTOCOL DATE: 26 OCTOBER 2021

INNOVATIONS STUDY NUMBER: BMT 29
VERSION 4

9.2 Clinician-Reported and Patient-Reported Global cGVHD Activity Assessments

Patients will be assessed for severity of cGVHD using the Clinician-Reported Global cGVHD Activity Assessment Form (Appendix E) and Patient-reported cGVHD Activity Assessment Form (Appendix F). Chronic GVHD severity will be assessed on Day 1 of each cycle and at the EOT visit.

9.3 Corticosteroid Use

Corticosteroid dose will be collected throughout the study according to the Schedule of Assessments (Appendix D) and changes will be documented. Please see Section 7.2 for additional details.

9.4 Quality-of-Life Impact

Quality of life impact will be assessed according to the Schedule of Assessments (Appendix D) using the Lee Symptom Scale (see Appendix I; Lee et al. 2002).

10. STATISTICAL CONSIDERATIONS

10.1 Statistical Design

This is a multi-center, open-label, single-arm pilot study of itacitinib in patients who have been receiving immunosuppressive therapy for the treatment of SR-cGVHD for a duration of >6 months prior to starting daily itacitinib treatment in this study. The study is designed to determine the ORR after 6 months of treatment with itacitinib.

10.2 Sample Size Considerations

No formal hypothesis testing is planned for this exploratory trial. In order to estimate the ORR in this population, a 95% exact two-sided confidence interval (CI) will be calculated. A sample size of 40 produces a two-sided 95% CI with a width equal to 0.266 when the sample proportion is 0.200 (i.e., 20% response rate).

10.3 Analysis Population

The following analysis populations will be used:

- The Response Evaluable Analysis Set is defined as all patients with cGVHD who received at least one cycle of itacitinib and completed at least one post-baseline disease assessment.
- The Safety Analysis Set is defined as all patients who received at least one dose of itacitinib.

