5.1.1 Primary Efficacy Period (Cycle 1 through End of Cycle 6)

The primary efficacy period is defined as Cycle 1 through the end of Cycle 6. A cycle is 28 days. Study treatment will begin on Cycle 1 Day 1 and study drug will be dispensed on Day 1 of each cycle.

Patients will be treated for a minimum of 6 cycles, unless they meet the discontinuation criteria listed in Section 3.3).

Primary efficacy assessments will be performed on Cycle 7 Day 1, after completion of 6 cycles of treatment.

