6.4 Response Assessments

Response criteria (CR, PR, or other [unchanged, mixed response, progression]) based on the 2014 NIH Consensus Development Project on Clinical Trials in cGVHD (see Appendix H for criteria) will be assessed on Day 1 of Cycles 2 through 7; and then every odd-numbered cycle thereafter starting on Day 1 of Cycle 9, as well as the EOT visit.

Patients with GVHD progression, progression of the underlying malignancy, or unacceptable toxicity should be discontinued from the study; patients with stable GVHD or a GVHD response to therapy will continue treatment.

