6.5 End-of-Treatment Visit

The follow-up evaluations required after treatment ends (due to the completion of the planned study treatment period, GVHD progression, progression of underlying malignancy, or once the patient is discontinued due to unacceptable toxicity or the decision to discontinue treatment by the patient or the study physician) are specified in Appendix D. This visit should be performed within 7 days and no later than 14 days after discontinuation of study treatment. If treatment is discontinued because of toxicity or any other reason(s) and no study treatment is administered, that visit may fulfill the EOT visit.

The following assessments will be performed at the EOT visit:

- Physical examination

CONFIDENTIAL

STUDY DRUG: INCB039110 (ITACITINIB)
FINAL PROTOCOL DATE: 26 OCTOBER 2021

INNOVATIONS STUDY NUMBER: BMT 29
VERSION 4

- ECOG performance status
- Vital signs (blood pressure, body temperature, and pulse rate after about 5 minutes of rest)
- Urine pregnancy test for women of child-bearing potential
- Blood transfusion review
- Electrocardiogram
- Hematology, lipid (fasting), and clinical chemistry panels
- Urinalysis
- Concomitant medication review
- AE and infection monitoring
- Global cGVHD activity assessment (clinician-reported [Appendix E] and patient-reported [Appendix F])
- cGVHD response assessment (Appendix H)
- Assess relapse of underlying malignancy with Lee Symptom Scale (Appendix I)
- Document corticosteroid dosage (total dose/kg and type of corticosteroids)
- Document concomitant cGVHD therapy

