10.4.2 Efficacy Analysis

All efficacy analyses will be performed using the Response Evaluable Analysis Set.

- ORR is defined as the proportion of patients with a cGVHD status of CR or PR after 6 months of treatment according to the NIH Consensus Criteria (Lee et al. 2015).
- Overall Survival (OS) is defined as the time from the first day of study drug administration (Day 1) to death on study. Patients who are alive will be censored at the date of last known date alive.

For ORR, the estimates and the associated 95% CIs (based on the Clopper-Pearson method) will be calculated.

For OS, a Kaplan-Meier curve will be generated and the median time to event and the associated 95% CIs will be provided.

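### The response rate and overall survival are analysed in a set that drops early failures, so the response rate can only be biased upward and Cycle 1 deaths can vanish from the survival curve

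*Combined protocol and SAP*

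**What the plan says.** Section 10.3 defines two sets. The Response Evaluable Analysis Set is "all patients with cGVHD who received at least one cycle of itacitinib and completed at least one post-baseline disease assessment". The other covers everyone treated: "The Safety Analysis Set is defined as all patients who received at least one dose of itacitinib".

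Section 10.4.2 then states: "All efficacy analyses will be performed using the Response Evaluable Analysis Set". That covers the primary endpoint, the proportion with complete or partial response after 6 months of treatment, reported with a Clopper-Pearson 95% interval. It also covers survival: "Overall Survival (OS) is defined as the time from the first day of study drug administration (Day 1) to death on study". Section 10.4.3 uses the all-treated set for safety only.

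On timing, Section 5.1.1 says "A cycle is 28 days" and "Primary efficacy assessments will be performed on Cycle 7 Day 1, after completion of 6 cycles of treatment". Section 6.4 says response "will be assessed on Day 1 of Cycles 2 through 7", so the first scheduled assessment is Cycle 2 Day 1. Section 6.5 and Appendix D (footnote k) add an end-of-treatment visit, with a response assessment, for patients who stop permanently.

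Section 10 contains no all-treated response rate, no rule counting early stoppers as non-responders, and no definition of what receiving one cycle means.

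**The concern.** Membership of the primary analysis set is decided after Day 1, and the patients it removes are those doing worst. There are two readings of the cycle condition.

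- **(a) A full 28 days.** Every patient who stops for good in Cycle 1 leaves the denominator, even one whose end-of-treatment assessment recorded progression.
- **(b) A cycle was started.** Only patients with no post-baseline assessment leave, such as early deaths or losses before the end-of-treatment visit.

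The plan does not choose between them. In an open-label trial the choice could be made after the data are known.

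The trial exists to estimate one response rate, and no control arm undergoes the same selection. An exclusion that removes only non-responders therefore moves the main result one way. Survival has a separate problem: its clock starts at the first dose, but entry to the set requires later events, so early deaths can be excluded from the curve meant to show them.

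**Working it through.** **Inputs.** N = 40 planned, 20% sample proportion and interval width 0.266 (Section 10.2); Clopper-Pearson 95% interval (Section 10.4.2); 28-day cycle and primary assessment at Cycle 7 Day 1 (Section 5.1.1); visit window of ±7 days (Appendix D). The number excluded, k, is not in the documents. It is assumed here to lie between 0 and 8 of 40; 8 is an upper scenario in which 20% are excluded.

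**Step 1: the plan's own figure.** For 8/40 the Clopper-Pearson interval is 0.0905 to 0.3565, width 0.2660. This matches the stated 0.266, so the stated precision uses a denominator of all 40.

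**Step 2: who can be excluded.** Routes out during Cycle 1 include death, withdrawal of consent, a need for additional systemic therapy (Section 3.3) and the Grade 4 discontinuation rule (Table 2). Under reading (a) the visit window adds another. Cycle 2 Day 1 is Study Day 29, and 29 − 7 = Day 22, so a patient stopped for progression at an early Cycle 2 visit has not had 28 days of drug.

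**Step 3: direction.** An excluded patient either stopped before completing one cycle or has no post-baseline assessment. Neither can have a response recorded after six cycles. The responder count x is unchanged, so x/(N−k) = (x/N) × N/(N−k), and the factor is never below 1. This takes evaluable patients who stop before month 6 as remaining in the denominator as non-responders. The plan does not say so, and dropping them too would raise the rate further.

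**Step 4: size, N = 40.**

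| k | Factor | 8 responders (95% CI) | 16 responders (95% CI) |
|---|---|---|---|
| 0 | 1.000 | 20.0% (9.1–35.6) | 40.0% (24.9–56.7) |
| 1 | 1.026 | 20.5% (9.3–36.5) | 41.0% (25.6–57.9) |
| 2 | 1.053 | 21.1% (9.6–37.3) | 42.1% (26.3–59.2) |
| 4 | 1.111 | 22.2% (10.1–39.2) | 44.4% (27.9–61.9) |
| 8 | 1.250 | 25.0% (11.5–43.4) | 50.0% (31.9–68.1) |

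The synopsis allows up to 40 patients, so enrolment may be lower. With N = 30 and 6 responders (20.0%), the rate becomes 20.7%, 21.4%, 23.1% and 27.3% for k = 1, 2, 4 and 8.

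**Step 5: coverage.** Let p be the true all-treated rate. Take X ~ Binomial(40−k, 40p/(40−k)) and find how often the interval computed on 40−k patients contains p.

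| k | p = 20% | p = 40% |
|---|---|---|
| 0 | 97.3% | 96.6% |
| 2 | 97.4% | 95.8% |
| 4 | 95.2% | 92.9% |
| 6 | 95.4% | 88.4% |
| 8 | 91.8% | 81.0% |

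**Step 6: survival.** Under reading (a), every patient in the set is alive at Day 28 by construction. With one or two Cycle 1 deaths among 40 treated, all-treated survival at Day 28 would be 39/40 = 97.5% or 38/40 = 95.0%. Under reading (b), a Cycle 1 death with no assessment is still left out.

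**The case against.** The strongest reply concerns size. Patients are planned to receive at least six cycles, non-response in the first two months leads to a dose increase rather than withdrawal, most rules in Table 2 begin with interruption or reduction, and eligibility screens out the sickest. All this points to a small k. At the planning rate of 20%, coverage stays above 95% through k = 6. The worst coverage shown, 81.0%, needs both a 40% response rate and 8 of 40 patients excluded, and nothing in the documents supports that loss. The trial is exploratory, with no hypothesis test, and Section 10.4.1 tabulates the number treated, so a reader could rebuild the all-treated rate. Reading (a) is not established, and the Day 22 example and the guaranteed survival to Day 28 depend on it. The effect on median survival, the summary actually planned, is not quantified.

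These points stand as limits on magnitude; they do not change the direction. A reader can re-divide the responder count but cannot reconstruct a Kaplan-Meier curve from a count of patients treated. There is also no reason to require response evaluability for survival. Adding the all-treated rate only as a supporting analysis would close part of the gap, but the headline would remain the figure with the avoidable bias.

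**Conclusion.** The concern holds. As written, the primary response rate is computed in a set that removes only non-responders, so it equals the all-treated rate times N/(N−k) and cannot be too low on this account. At the planning rate with 40 treated, the overstatement is 0.5 to 1.1 percentage points for k = 1 or 2, 2.2 points for k = 4 and 5.0 points for k = 8. It is small for likely values of k and material only for larger ones. Overall survival can lose Cycle 1 deaths on either reading of the cycle condition. No test or decision threshold is affected. The direction follows from the plan's own definitions; the size rests on an assumed k. This should be corrected, though it does not undermine the trial.

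**What to change.** In Sections 10.3 and 10.4.2:

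- Make the Safety Analysis Set (all patients with at least one dose) the primary set for the response rate, and use it for overall survival.
- Count any patient without a complete or partial response at the Cycle 7 Day 1 assessment as a non-responder, whatever the reason.
- Keep the Response Evaluable rate as a sensitivity analysis.
- Define the cycle condition, for example as 28 days on study treatment or as any dose in Cycle 1.

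Section 10.2 needs no change, since its 0.266 width already assumes all 40 patients. The cost is one or two sentences, with no new data, visits or patients. The one downside is that the reported response rate may be slightly lower.
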